1.1. Specific Aims

Aim #1: Determine the effectiveness of an online, CBT-based pain management program and virtual coach-led (telephonic/video) CBT-CP on achieving clinically meaningful improvements ($\geq 30\%$) in patients' pain severity (pain intensity + pain-related interference) relative to those receiving usual care at 3 months from randomization.

1a. Examine the impact of the active interventions on secondary pain outcomes and related quality of life outcomes (social role functioning, physical functioning, and patient global impression of change); as well as exploratory outcomes, which include long-term opioid use, comorbid symptomology (depression, anxiety, and sleep disturbance), and high impact and graded chronic pain.

1b. Conduct subgroup analyses to determine the impact of the active interventions on specific populations and explore for potential heterogeneity of treatment effects by sex; rural/medically underserved residency; multiple pain conditions; mental health mood disorders; and negative social determinants of health.

1c. Examine the role of theory-based mediators, pain catastrophizing, pain-related self-efficacy, and perceived support, on pain-severity.

Aim #2: Assess the cost and incremental cost-effectiveness of the online and virtual coach-led CBT-CP interventions compared to each other and usual care.

Aim #3: Conduct a qualitative evaluation to understand: 1) patient experiences of the interventions, including how they relate to treatment response, variability by site, and rural/medically underserved residency status; and 2) health system issues, including

adaptations and contextual factors at the site and external levels, barriers and facilitators to intervention success and potential for adoption, sustainability and dissemination.

NOTE: The analytic approaches for Aims #1-2 are the focus of this Statistical Analysis Plan (SAP). Aim #3 is a qualitative evaluation and does not utilize statistical analyses; therefore, it is not addressed in this SAP.

1.2. Study Population

The 2,331 participants we will randomize (777 per study arm) will include those who receive primary care services from 4 integrated health care systems/clinical sites: KPGA, KPNW, KPWA and Essentia Health and who have high-impact chronic pain as demonstrated by electronic health records (EHR)-based eligibility criteria and a screening assessment.

1.3. Description of Interventions

Two interventions will be tested in this comparative effectiveness trial.

- 1) An online, CBT-based pain coping skills training program (painTRAINER)
- 2) A virtual, live, coach-led CBT-CP intervention (telephone and/or video-administered)

Both interventions are comprised of 8 sessions which participants are expected to complete weekly. The content of the 2 interventions is analogous and focuses on interactive training in evidence-based pain-coping skills.

Our analysis will include an economic evaluation comparing the costs, and incremental cost-effectiveness of the active interventions. We expect that the live coach and other elements of the virtual, coach-led intervention will make it more expensive (and possibly more effective) than the online intervention (painTRAINER).

Those randomized to the usual care arm of the study will be sent a bound copy of the 2020 edition of the *American Chronic Pain Association Resource Guide to Chronic Pain Management*.

All enrollees can receive any pharmacologic (prescription or over the counter) and nonpharmacologic treatments available to them without restriction.

2.0. Introduction

This Statistical Analysis Plan (SAP) provides the details of statistical considerations, analyses, and reports planned for the RESOLVE study, including proposed regression models, sample size estimates, power considerations, and safety analyses. The proposed analyses will be conducted on the entire participant sample and on pre-specified subgroups, as described in this SAP. In addition, this plan discusses statistical issues relevant to these analyses (e.g., sample data to be used, missing data, adjustments for multiplicity, etc.).

For the HEAL Pain ERN, the Data Coordinating Center (DCC) at the University of Utah has the primary responsibility for data quality. For safety analyses and DSMB report production, the JHU-Tufts Statistical Core, physically located at the Johns Hopkins University will examine or oversee data quality, create secondary variables, and perform exploratory data analyses (EDA).

All variables in the analytic database will be evaluated to detect gaps, patterns, and inconsistencies in the data. These analyses will emphasize examination of the nature and extent of variability for all variables. Visual techniques to explore continuous variables may include histograms and boxplots. Outliers will additionally be examined for data entry errors. Summary statistics for continuous variables will include the number of patients, median, mean, standard deviation, and range, while statistics for categorical variables will include the frequency and percentage of patients in each category.

Statistical analyses will be performed on data that have been quality-assured through DCC and Statistical Core protocols and monitoring reviews, and that have been exported directly from the RESOLVE study database. The following analysis procedures may be applied to blinded (no treatment arm designation, for study investigators and staff), partially unblinded (treatment designation only as "A", "B", or "C" for DSMB and at interim analyses), and unblinded (full treatment designation, for final analyses) data, by Statistical Core and DCC staff having the appropriate role permissions.

All data collection procedures and statistical analyses in this SAP will be finalized and approved by the RESOLVE Study Principal Investigator (PI) and Study Lead Statistician prior to the unblinding of the data. In addition, the data collection procedures and statistical analyses detailed in this SAP may be modified and are given precedence over the analytical plans outlined in the Study Protocol; however, any modifications or changes in the primary endpoint and/or its analysis will also be reflected in a protocol amendment. Any updates to the SAP will be thoroughly detailed and documented at the beginning of this document.

3.0. Study Outcomes

3.1. Primary Effectiveness Trial Outcome

Primary Outcome	Brief Description of Measure	Outcome Measured By	Time Frame
Achieving minimal clinically important difference (MCID) in pain severity at 3 months (Yes / No)	Minimal clinically important difference (MCID) in pain severity is defined as a 30% decrease in score on modified 11-item version of the Brief Pain Inventory – Short Form (BPI-SF) ¹⁻³ from baseline (consistent with IMMPACT consensus guidelines) ⁴ (binary)	Patient self-reported pain at baseline and 3 months	Baseline to 3 months

3.2. Secondary Effectiveness Trial Outcomes

Secondary Outcomes	Brief Description of Measure	Outcome Measured By	Time Frame
Achieving MCID in pain severity at 6 and 12 months (Yes / No)	See above (binary)	Patient self-reported pain at baseline, 6 and 12 months	Baseline to 6 and 12 months
Achieving MCID in pain intensity (Yes / No)	Minimal clinically important difference (MCID) in pain intensity is defined as a 30% decrease in score on 4-item pain intensity subscale of the Brief Pain Inventory – Short Form (BPI-SF) ¹⁻³ from baseline	Patient self-reported pain at baseline, 6 and 12 months	Primary: Baseline to 3 months Secondary: Baseline to 6 and 12 months
Achieving MCID in pain-related interference (Yes / No)	Minimal clinically important difference (MCID) in pain intensity is defined as a 30% decrease in score on 7-item pain-related interference subscale of the Brief Pain Inventory – Short Form (BPI-SF) ¹⁻³ from baseline	Patient self-reported pain at baseline, 6 and 12 months	Primary: Baseline to 3 months Secondary: Baseline to 6 and 12 months
Pain severity	BPI-SF; composite of pain intensity (4 items) and pain-related interference (7 items) subscales (11 items; continuous)	Patient self-reported pain at baseline, 3, 6 and 12 months	Primary: Baseline to 3 months Secondary: Baseline to 6 and 12 months
Pain intensity	Pain intensity subscale of the BPI-SF (4 items; continuous)	Patient self-reported pain at baseline, 3, 6 and 12 months	
Pain-related interference	Pain-related interference subscale of the BPI-SF (7 items; continuous)	Patient self-reported pain at baseline, 3, 6 and 12 months	Primary: Baseline to 3 months Secondary: Baseline to 6 and 12 months

Secondary Outcomes	Brief Description of Measure	Outcome Measured By	Time Frame
Social role functioning	PROMIS Ability to Participate in Social Roles 4A ⁵ (4 items; continuous)	Patient self-reported social role functioning at baseline, 3, 6 and 12 months	Primary: Baseline to 3 months Secondary: Baseline to 6 and 12 months
Physical functioning	PROMIS Physical Functioning Short Form 6b (6 items; continuous)	Patient self-report physical functioning at baseline, 3, 6 and 12 months	Primary: Baseline to 3 months Secondary: Baseline to 6 and 12 months
Patient global impression of change (PGIC)	Guy/Farrar Patient Global Impression of Change (1 item each for pain status and overall status)	Patient self-reported impression of change at 3, 6 and 12 months	Primary: Baseline to 3 months Secondary: Baseline to 6 and 12 months

3.3. Exploratory (Tertiary) Effectiveness Outcomes

Exploratory (Tertiary) Outcomes	Brief Description of Measures	Measured By	Time Frame
Long-term opioid use (Yes / No)	Opioid prescription orders or fills indicating a continuous ≥ 60-day supply during the prior 90-day period; account for prescriptions prior to 90-day look-back which carry into the assessment period (binary)	Electronic health record (EHR) opioid prescription data assessed quarterly 90-Day Periods for Developing Quarterly Variables (Baseline survey date = Day 1) Baseline = Day -90 to day -1 3 months = Day 1 to day 90 6 months = Day 91 to day 180 9 months = Day 181 to day 270 12 months = Day 271 to day 360	Baseline to 3, 6 and 12 months
Depression symptomology	Patient Health Questionnaire-8 (PHQ-8) ⁶ (8 items; continuous)	Patient self-reported depression symptomology at baseline, 3, 6 and 12 months	Baseline to 3, 6, and 12 months
Anxiety symptomology	Generalized Anxiety Disorder-7 (GAD-7) ⁷ (7 items; continuous)	Patient self-reported anxiety symptomology at baseline, 3, 6 and 12 months	Baseline to 3, 6, and 12 months
Sleep disturbance	PROMIS Sleep Disturbance – Short Form 6a ⁸ (6 items; continuous)	Patient self-reported sleep disturbance at baseline, 3, 6 and 12 months	Baseline to 3, 6, and 12 months

Exploratory (Tertiary) Outcomes	Brief Description of Measures	Measured By	Time Frame
Examine the impact of the active interventions on high impact chronic pain and graded chronic pain	High Impact Chronic Pain ^{9,10} Graded Chronic Pain Scale-Revised ¹⁰	Patient self-reported pain intensity, duration, and pain-related disability	Baseline to 3, 6, and 12 months

3.4. Economic Evaluation Outcomes

Cost Outcomes	Brief Description of Measures	Measured By	Time Frame
Cost and incremental cost-effectiveness	Health care utilization and intervention costs will be assessed. Using the framework of cost-effectiveness, we will estimate the incremental cost per additional patient with a MCID in pain severity (30% reduction from baseline), at 12 months, and the quality-adjusted life year (QALY) gained—utilities will be estimated using the EQ-5D-5L. ¹¹	Healthcare utilization costs: EHR data costed using standard costing algorithms ^{12,13} and Medicare fee schedules Intervention costs: Process data related to all relevant resources used in the intervention delivery EQ-5D-5L: Patient self-report at baseline, 3-, 6- and 12-months	Patient health care utilization costs from baseline to 12 months

4.0. Additional Variables for Effectiveness Analyses (Moderators and Mediators)

The following **moderators** will be assessed related to the **primary outcome**.

Moderator	Definition	Data Source
Sex	Male vs. Female/Other Sex at birth as reported by subject; assessed using HEAL CDE Demographic question	Patient self-report at baseline
Age	<65 vs ≥ 65 years old	EHR data
Race/Ethnicity	White/Non-Hispanic Black or African American/Non-Hispanic Hispanic Other	Patient self-report at baseline
Rural/medically underserved residency	Urban vs. Rural/medically underserved Rural is defined as subject's resident Census Tract corresponds to US Census 2010 Rural-Urban Commuting Area (RUCA) Codes 4, 5, 6, 7, 8, 9 or 10 (https://www.ers.usda.gov/data-products/rural-urban-commuting-area-codes/documentation/) Medically underserved is defined as subject's resident Census Tract corresponds to HRSA-designated primary care or mental health geographic or geographic high needs health professional shortage area (https://data.hrsa.gov/tools/shortage-area/hpsa-find)	EHR patients' geocoded data extracted at baseline
Multiple non-malignant musculoskeletal pain conditions	1 pain cluster vs. >1 > 1 pain-related ICD-10 diagnosis corresponding to more than one (>1) of the non-malignant musculoskeletal chronic pain condition clusters developed for the National Pain Strategy chronic pain condition clusters ¹⁴ 1. Back pain 3. Neck pain 4. Limb/extremity pain, joint pain and arthritic disorders 5. Fibromyalgia 6. Headache 7. Orofacial, ear, and temporomandibular disorder pain 8. Musculoskeletal chest pain 9. General pain subcategory of the Other painful conditions cluster	EHR data; diagnoses in subject's EHR extracted at baseline for prior 360 days
Mental health mood disorders	ICD-10 diagnosis for depression and/or anxiety diagnosis	EHR data; diagnoses in subject's EHR extracted at baseline for prior 360 days

Moderator	Definition	Data Source
Negative social determinants of health (SDOH)	
Negative SDOH/existing need vs. No SODH need
 
Patient endorses need in one or more of the following domains.
 
Financial Resource Strain (1 item)
 
Food Insecurity (2 items)
 
Transportation/Access Needs (2 items)
 
Housing Instability (3 items)
	Patient self-report at baseline

The following **mediators** will be assessed related to **the primary outcome**.

Mediator	Brief Description of Measure	Measured By
Pain catastrophizing	Pain Catastrophizing Scale (PCS)– Short Form 6 ¹⁵ (6-item; continuous)	Patient self-report at baseline and 3 months
Pain self-efficacy	Self-Efficacy for Pain Management subscale of the Chronic Pain Self-Efficacy Scale ¹⁶ (5-item; continuous)	Patient self-report at baseline and 3 months
Perceived support	2 items; developed in UG3 phase	Patient self-report at notification of randomization and 3 months

5.0. Sample Size Determination for the Primary and Secondary Effectiveness Analyses

For our primary study outcome, clinically meaningful improvement (MCID; 30% reduction in overall BPI-SF score) in pain severity at 3 months, we calculated sample size requirements for a two-sided comparison of independent proportions with 90% power using Fisher's Least Significant difference method to account for three-way comparisons (specifically conduct Omnibus Wald Test for any difference between three groups and then conduct pairwise comparisons given an overall difference is statistically significant at the 0.05 alpha level). Sample size calculations assumed a usual care outcome rate of 15% who achieve the MCID of 30% reduction in pain severity from baseline to 3 months. The 15% usual care rate was chosen because we observed this rate among participants in the usual care arm of our recently completed PPACT trial¹⁷ and it is similar to rates observed by others in the usual care arm of similar trials.¹⁸ We calculated the necessary sample size of 1,863 (621 per arm) to detect a difference of 7.5% between a given intervention group relative to usual care in the proportion of individuals who attain a clinically meaningful change (30% reduction from baseline) in pain severity. We estimate a retention rate of 80%. Thus, to achieve this final sample size, we will randomize 2,331 individuals, 777 per intervention arm. A 7.5% detectable difference corresponds to 22.5% (relative change of 150%) of individuals in an intervention arm attaining a clinically meaningful change in pain severity.

We also estimated power for secondary analyses related to aim 1b (subgroup analyses). We calculated sample size requirements for these secondary analyses using the same assumptions described above (i.e., a two-sided comparison of independent proportions using Fisher's Least Significant difference approach to account for three-way comparisons, with sample size calculations assuming an improvement rate of 15% in the usual care arm). We ranged our subgroup sample size between 20% and 40% of the original 1,863 sample size since this should cover the range of the subgroup sample sizes of interest.

Power for Subgroup Analyses Ranging the Size of the Subgroup

Assumptions		80% Power to Detect:		
Subgroup Sample Size	Usual Care (UC)	Intervention (Int)	Detectable Difference	Relative Change
N (% of 1,863)	% UC	% Int	% Int - %UC	% Int / %UC
372 (20%)	15.0%	31.0%	16.0%	206.7%
558 (30%)	15.0%	27.7%	12.7%	184.7%
744 (40%)	15.0%	25.8%	10.8%	172.0%

We have 80% power to detect a 10.8% difference (relative change of 172%) between each intervention group and UC if subgroup sample size is 40% of the overall study population and 16.0% difference (relative change of 206.7%) if the subgroup sample size is 20% of the overall study population.

Note that in our previous studies we observed for sex, comorbid mental health conditions (depression, anxiety) not to be less than 40% of our population suggesting that we have high power for our primary subgroups of interest. Further, we are aiming to have at least 20% of rural/medically underserved residency and therefore we have good power for this subgroup. Negative social determinants of health is an exploratory subgroup since we are not sure how many people in this population a priori will have this indication.

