6 RECRUITMENT PROCEDURES AND RETENTION STRATEGIES

6.1 Recruitment of Patients

Each of the 4 sites will be responsible for recruiting and enrolling approximately 595-625 patients per site but the final number will vary slightly across sites. In order to reach the overall study target for number randomized within the study timeline, some sites may enroll more than others (i.e., Essentia and KPGA vs. KPWA). [Note: The study aims to randomize 2,331 individuals (at least 777 per arm) and, as such, the number needed to enroll may be larger than the 2,500 target as not all who consent/enroll go on to be randomized.] Study activities from recruitment through completion of baseline survey will be completed by each site for their population of patients.

For recruitment, each site will query their EHR data warehouses to identify a sample of patients who meet the EHR-based inclusion criteria on a set frequency. The sample of patients will be stratified by urban vs. rural or medically underserved residence, based on the individuals' resident Census Tract/geocoded data in the EHR. The table below provides definitions to be used for these categories.

Urban	Rural or Medically Underserved (MUA)
Urban is defined as subject's resident Census Tract corresponds to US Census 2010 Rural-Urban Commuting Area (RUCA) Codes 1, 2 or 3 (https://www.ers.usda.gov/data-products/rural-urban-commuting-area-codes/documentation/)	Rural is defined as subject's resident Census Tract corresponds to US Census 2010 Rural-Urban Commuting Area (RUCA) Codes 4, 5, 6, 7, 8, 9 or 10 (https://www.ers.usda.gov/data-products/rural-urban-commuting-area-codes/documentation/) Medically underserved (MUA) is defined as subject's resident Census Tract corresponds to HRSA-designated primary care or mental health geographic or geographic high needs health professional shortage area (https://data.hrsa.gov/tools/shortage-area/hpsa-find)

Then, a random sample of approximately 500-700 patients per month per site will be generated, with adjusted sampling for rural residency to ensure at least 20% in either the urban or rural/MUA subgroup at each site. Specifically, individuals who reside in rural or medically underserved areas will comprise 30-50% of the overall RESOLVE study population. Each site will have at least 20% enrollment in either subgroup (urban vs. rural/MUA) to enable sufficient sample size for subgroup analyses.

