744 (40%)	15.0%	25.8%	10.8%	172.0%

There is 80% power to detect a 10.8% difference (relative change of 172%) between each intervention group and UC if subgroup sample size is 40% of the overall study population and 16.0% difference (relative change of 206.7%) if the subgroup sample size is 20% of the overall study population.

Note that in previous studies of this study team, sex, and comorbid mental health conditions (depression, anxiety) were not less than 40% of the population suggesting there is high power for the primary subgroups of interest. Further, the study is aiming to have at least 20% of rural/medically underserved residency and therefore there is good power for this subgroup. Individuals with negative social determinants of health comprise an exploratory subgroup since it is not clear how many people in this population *a priori* will have this indication.

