16.0. Additional Effectiveness Analyses for Primary Outcome (Moderators and Mediators)

Moderator (Aim 1b) Statistical Hypotheses: We hypothesize that for patients with more complex conditions (concomitant mood or anxiety disorders; multisite pain) or challenging social / environmental factors (rural/medically underserved or unmet social needs) the contact with a live coach will result in better pain-severity outcomes when compared to those receiving painTRAINER.

Moderator (Aim 1b) Analyses: Subgroup analyses will be conducted to determine the impact of the active interventions on specific populations and explore for potential heterogeneity of treatment effects by sex, age, race/ethnicity, rural/medically underserved residency, multiple pain conditions, mental health mood disorders, and negative social determinants of health. Analyses for Aim 1b will follow the same general approach as for Aim 1 but will be focused on assessing heterogeneity of treatment effects (sub-groups). We will assess heterogeneous treatment effects by each potential moderator separately. For each moderator, we will include in the regression models described in the analytic plan for Aim 1, a main effect for the moderator and an interaction between the moderator, intervention, and follow-up time, to estimate time-specific intervention effects within each subgroup defined by the potential moderator. The primary comparison for Aim 1b will be of the interaction terms associated with each intervention arm at the 3-months follow-up time. The longitudinal nature of data collection will allow us to qualitatively assess if the treatment effectiveness pattern is different over time in each of the intervention groups at the two levels of each of the moderators.

Mediator (Aim1c) Statistical Hypotheses: We hypothesize that changes in pain catastrophizing, pain-related self-efficacy, and perceived support from baseline to 3 months will be mediators of treatment outcomes at 6 months for those in both active interventions.

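### The high and good power stated for the Aim 1b subgroups holds only for large effects versus usual care within a subgroup; no power is given for the interaction named as the primary comparison or for coach versus painTRAINER

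*SAP*

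**What the plan says.** SAP 5.0 and Protocol 15.1 give the same subgroup power table: usual care 15%, two-sided comparison under Fisher's LSD, 80% power. The detectable intervention rates are 31.0% (N = 372, 20% share), 27.7% (N = 558, 30%) and 25.8% (N = 744, 40%). The contrast is labelled: "We have 80% power to detect a 10.8% difference (relative change of 172%) between each intervention group and UC" for the 40% row.

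For sex and mental health conditions, expected to be at least 40% of the sample, the SAP concludes "suggesting that we have high power for our primary subgroups of interest" and the protocol "suggesting there is high power for the primary subgroups of interest". For rural/medically underserved residency the protocol says "the study is aiming to have at least 20% of rural/medically underserved residency and therefore there is good power for this subgroup", and the SAP likewise ends "therefore we have good power for this subgroup". Protocol 6.1 plans a larger overall share: "individuals who reside in rural or medically underserved areas will comprise 30-50% of the overall RESOLVE study population".

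SAP 16.0 defines the test: "The primary comparison for Aim 1b will be of the interaction terms associated with each intervention arm at the 3-months follow-up time". Protocol 15.7 matches it. The hypothesis in both is that, in patients with complex conditions or difficult circumstances, the coach does better than the online program. In SAP 14.0 the model's reference group is usual care. Neither document gives a power or a detectable size for an interaction, or for coach versus painTRAINER.

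**The concern.** The table answers one part of Aim 1b: how large an effect versus usual care must be inside a subgroup to be detected. The power statement is then made for the subgroups in general, while the comparison called primary is a difference between subgroups. At a given effect size, that difference is estimated less precisely than the effect inside one subgroup.

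A reader who trusts the adjectives may take a null moderator result as evidence that the effect is the same across subgroups, when the design could detect only large differences. It is also unsettled which contrast carries the hypothesis. Leaving that open until unblinding allows a choice after the results are known.

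**Working it through.** **Inputs.** Two-sided 0.05, with an omnibus Wald test and then pairwise tests (SAP 10.0). Usual care 15%, design effect 7.5 points (22.5%), 621 analysable per arm (SAP 5.0). Equal allocation (SAP 8.0). Subgroup sizes per arm: 372/3 = 124, 558/3 = 186, 744/3 = 248; for a 50% share, about 310.

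**1. Reproduce the table.** Simulate binomial arms. With l = ln(p̂) and variance (1−p̂)/(n·p̂), require the 2-df omnibus statistic to exceed 5.99 and the pairwise z to exceed 1.96, both active arms at the alternative rate. Results: 80% in each of the three rows, and 90.5% for 621 per arm at 15% versus 22.5%. The table and the primary calculation both stand.

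**2. Compare with the design effect.** 10.8/7.5 = 1.44; 12.7/7.5 = 1.69; 16.0/7.5 = 2.13. Power within a subgroup at 15% versus 22.5%:

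| Share (n per arm) | Gated, both arms effective | Gated, one arm effective | Pairwise test, no gate |
|---|---|---|---|
| 20% (124) | 21.3% | 24.4% | 31.0% |
| 30% (186) | 34.6% | 37.8% | 44.9% |
| 40% (248) | 47.2% | 50.1% | 56.5% |
| 50% (310) | 58.4% | 61.1% | 66.5% |

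Hand check of the 40% ungated cell: SE = √[0.85/(248×0.15) + 0.775/(248×0.225)] = √(0.02285 + 0.01389) = 0.192; ln(1.5)/0.192 = 2.12; Φ(2.12 − 1.96) ≈ 56%. The plan uses the gate, so the gated columns apply.

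**3. Interaction versus usual care.** The documents give no subgroup-specific rates, so these are assumptions: usual care 15% in both strata, 621 per arm, 40% share (248.4 inside, 372.6 outside), no covariates, no coach clustering, no omnibus gate. On the planned log scale, SE² is the sum of (1−p)/(n·p) over the four cells, and power = Φ(ln R/SE − 1.96), where R is the ratio of risk ratios. On the risk-difference scale the variance terms are p(1−p)/n. Three ways to place a 7.5-point difference between strata:

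- Coach 22.5% inside, 15% outside: ln(1.5) = 0.405, SE 0.259, power 35%; risk difference 0.075/0.0436, power 41%.
- Coach 27% inside, 19.5% outside (average 0.4×27 + 0.6×19.5 = 22.5%): 0.325/0.245, power 26%; risk difference 0.075/0.0455, 38%.
- Coach 30% inside, 22.5% outside: 0.288/0.238, power 23%; risk difference 0.075/0.0466, about 36%.

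If the table's full 10.8 points existed inside a 40% subgroup and nothing outside, interaction power would be 57% (log scale) or 68% (risk difference), not 80%.

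**4. Coach versus painTRAINER.** Write γC and γP for the 3-month moderator interactions of coach and painTRAINER. Each is measured against usual care. In γC − γP the usual-care terms cancel, leaving ln(coach/painTRAINER) inside minus the same outside. With 30% versus 22.5% inside and 22.5% in both arms outside: 0.288/0.204, power 29%; risk difference 0.075/0.0498, power 32%.

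**5. Detectable ratio of risk ratios at 80% power.** Solve ln R = 2.80 × SE, updating the cell rates. Shares of 20/30/40/50%:

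- Versus usual care: 2.25/2.08/2.01/2.01 (coach 15% outside) or 2.13/1.97/1.90/1.89 (coach 22.5% outside).
- Coach versus painTRAINER: 1.90/1.78/1.73/1.73 (both 22.5% outside, painTRAINER 22.5% inside) or 2.25/2.08/2.01/2.01 (both 15% outside, painTRAINER 15% inside).

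The design's main-effect risk ratio is 22.5/15 = 1.5.

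**The case against.** The strongest defence is that the plan prints its detectable differences, labels them as versus usual care, and links the adjectives to them through subgroup share: *high* to shares of at least 40%, *good* to at least 20%. It never claims 80% power for 7.5 points within a subgroup; that benchmark is mine, and lower power in part of the sample is expected. It also claims no figure for interactions. All of that is true. A reader might infer that the table is wrong, or that the plan asserts interaction power; the documents support neither. What remains is that the adjectives are given as conclusions about Aim 1b, hold only at 1.4 to 2.1 times the design effect, and concern a contrast other than the one named as primary.

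A reader might also see a conflict between the 20% rural share and the planned 30–50%. There is none: 20% is a floor, and the 30% and 40% rows fit the plan better. So the 20% row, and the 2.1 multiple, is a floor case.

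Finally, the SAP 16.0 sentence can be read as comparing the two arms' interaction terms with each other, which would already be the right contrast. It can equally mean each term tested on its own against usual care. It therefore does not follow that the plan fails to test its hypothesis, only that the text leaves it unclear.

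**Conclusion.** The concern holds as a misleading design statement together with an ambiguous contrast. Within a subgroup versus usual care, gated power at 7.5 points with both arms effective is 21.3%, 34.6% and 47.2% for shares of 20%, 30% and 40%, and 58.4% at 50%; these figures use only the plan's inputs. The interaction figures (about 23–41% versus usual care and 29–32% for coach versus painTRAINER, at a 40% share) rest on my assumed rates and show the order of magnitude, not an error in a printed number. Coach clustering would lower them; covariate adjustment might raise them slightly.

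It would go too far to infer that the trial is underpowered for its main question: the primary calculation reproduces and is untouched. Confidence intervals will also show what a null subgroup result excludes, which limits the harm. The correction should be made, but nothing in the sample or model depends on it.

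**What to change.** 1. In SAP 5.0, and in Protocol 15.1 at its next amendment, remove the two power adjectives. State that 80% power applies only to the tabulated within-subgroup differences versus usual care. For rural/underserved residency, cite the 30% and 40% rows that match the planned share, with 20% as the floor.
2. Add that power for the Aim 1b interaction is limited, with the detectable ratio of risk ratios and its assumptions: about 1.9–2.3 versus usual care and about 1.7–2.3 for coach versus painTRAINER.
3. In SAP 16.0, specify that the hypothesis is tested by coach-by-moderator minus painTRAINER-by-moderator at 3 months. Each arm's interaction against usual care does not by itself test it.

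If Protocol 3.4 is cited for the exploratory status of the moderators, note that it sets them at 6 months, whereas Protocol 15.7 and SAP 16.0 use 3 months.

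The cost is wording and one short calculation, with no change to the sample or model. SAP 2.0 gives the SAP precedence over the protocol's analysis text, so the SAP edit suffices for now; the protocol edit needs IRB review (Protocol 19.2) and can wait. The downside is a less favourable power statement.
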